5.3 RANDOMISATION

Patients will be randomised by remote computer to ensure allocation concealment. Allocation will be in a 1:1 ratio stratified by centre in blocks. The randomisation sequence will be generated by an independent statistician.

6 STUDY ASSESSMENTS

6.1 STUDY ASSESSMENTS AND MANAGEMENT DURING THE INTERVENTION

6.1.1 Duration on intervention

The intervention period will last from the time of enrolment until discharge from the acute hospital.

The intervention will end when one of the following occurs:

- 1. Patient is discharged home from hospital (or to a family member/friend who plan to provide support/care post-acute hospital discharge)
- 2. Patient dies during the acute hospital stay
- 3. Patient is discharged to a rehabilitation hospital or facility
- 4. Patient is discharged to an intermediate or long-term care facility

Note: If a participant is discharged to another acute care hospital from the enrolling hospital as part of the same hospitalisation, the randomisation allocation will be maintained wherever possible until discharge from that acute hospital. The site study team will attempt to provide advice to the hospital to which the patient is discharged and obtain relevant study assessment data. Continuing to follow up these patients for primary outcome data at 90 days is the priority.

6.1.2 Assessment and management during intervention period

The local care and research teams, in accordance with the protocol, will carry out the management of the patient during the intervention period.

6.1.2.1 Measurement of haemoglobin concentration:

Measurement of haemoglobin concentration in the acute hospital will be at the discretion of the clinical teams unless haemoglobin concentration is not measured as part of routine care for seven consecutive days.

If seven days have passed since the previous haemoglobin concentration measurement, the research team will request that the clinical team undertakes a measurement. This will only apply during the intervention period.

6.1.2.2 Transfusion practice during the intervention for patients randomised to the usual care transfusion practice

Patients should be managed according to current NICE guidance (see: www.nice.org.uk/guidance/ng24/chapter/Recommendations#red-blood-cells-2)

For the purpose of the trial this means:

Use restrictive red blood cell transfusion thresholds for patients who need red blood cell transfusions and who do not have major haemorrhage or have acute coronary syndrome.

Use a threshold of less than 70 g/litre and a haemoglobin concentration target of 70–90 g/litre after transfusion, unless the responsible clinician decides to modify this based on the patients' condition.

Use single-unit red blood cell transfusions for adults who do not have active bleeding and recheck Hb within 24-48 hours of the transfusion

This guidance should be followed after each haemoglobin concentration measurement undertaken during the intervention period (minimum one measurement per seven days).

6.1.2.3 Transfusion practice during the intervention for patients randomised to the intervention (more liberal) transfusion practice

Patients should be managed as follows following each haemoglobin concentration measurement undertaken during the intervention period:

If the haemoglobin concentration is ≥100g/L no transfusion should be given.

If the haemoglobin concentration is <100g/L a single-unit red blood cell transfusion should be given followed by clinical reassessment and re-checking the haemoglobin concentration.

If the haemoglobin concentration remains <100g/L further single unit red blood cell transfusions should be given until the haemoglobin concentration is 100-120g/L.

For both study groups, the haemoglobin concentration should be re-checked after each unit of red blood cells they receive unless they are bleeding (NICE Blood Transfusion Quality Statement 3: www.nice.org.uk/quidance/gs138/chapter/Quality-statements)

Haemoglobin concentration should ideally be re-checked within 24 hours of each transfusion and definitely within 48 hours. *If Haemoglobin is not re-checked within 48 hours this should be reported as a deviation.*

6.1.2.4 Transfusion prescription and patient monitoring during transfusion

Prescription of RBC transfusions should be made by a member of the clinical team using local procedures and documentation. Transfusions should be commenced **as soon as possible** after a triggering Hb result (the time the sample was taken as per the laboratory report), **and within a maximum of 48 hours**. Transfusions that do not occur or occur after 48 hours will be considered a protocol deviation (see 6.1.3). Bedside prescription checking and monitoring of patients during the transfusion period should follow locally agreed protocols and Standard Operating Procedures. This may include prescription of additional medication, such as diuretics, at the discretion of the clinical team.

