- 6. Consent provided (by participant or in accordance with appropriate mental capacity legislation for the site)

Exclusion criteria

- 1. Contraindication or objection to RBC transfusion
- 2. Active bleeding when screened
- 3. Primary neurological ICU admission diagnosis, including primary brain or spinal cord injury
- 4. Patients discharged from the ICU following cardiac surgery
- 5. Currently receiving or planned to receive end-of-life care
- 6. Not expected by clinical team to survive to hospital discharge.
- 7. Patient with a proven chronic haematological disease that requires regular RBC transfusion to treat anaemia
- 8. Patient with dialysis-dependent chronic renal failure prior to ICU admission
- 9. Patient receiving regular erthyropoietin (or any erythropoiesis stimulating agent) treatment for anaemia prior to ICU admission.
- 10. Unable to obtain consent (from patient or in accordance with appropriate mental capacity legislation for the site)
- 11. Readmission to ICU during current hospitalisation episode and not enrolled following previous ICU admissions
- 12. Patient recovering following liver transplantation, kidney transplantation, or combined kidney/pancreas transplantation
- 13. Patient recovering from variceal bleeding due to chronic liver disease
- 14. Prisoners
- 15. Patient due for imminent hospital discharge within the next 24 hours

RANDOMISATION: Allocation 1:1 by remote computer randomisation (stratified by centre in blocks).

TREATMENT GROUPS:

Intervention group: All patients will receive a single unit RBC transfusion post-randomisation. Single RBC transfusions will subsequently be administered to achieve and maintain Hb 100-120g/L until hospital discharge. Hb measured at least weekly in hospital. Hb transfusion trigger <100g/L

Comparator 'usual care' group: Current usual care transfusion practice, namely single RBC transfusions when Hb less than 70g/L (or modified according to clinician decision) to achieve target Hb 70-90g/L. Hb measured at least weekly in hospital.

Co-interventions: all other aspects of care will be according to clinician decisions. Other treatments for anaemia, such as iron therapy, will be permitted in both groups but decided by treating clinicians.

Duration of intervention: From randomisation until acute hospital discharge (typically 2-3 weeks).

OUTCOMES:

Primary outcome: Physical Component Score (PCS) of the SF-36 HRQoL questionnaire at 90 days post-randomisation.

Secondary outcomes:

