5.1.2 Eligibility period

The eligibility window will be from the time the patient meets inclusion criteria and has no exclusion criteria for up to seven days following the decision by the treating clinician that the patient is **ready for ICU discharge**, as long as the patient remains in the acute hospital. The aim will be for enrolment to occur as close to ICU discharge as possible, but recognises that patients are often fatigued and/or may need time to consider participation during this period.

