5.1.3 Haemoglobin concentrations during screening and eligibility period

A patient can be screened as eligible for the trial based on any haemoglobin concentration during the eligibility period. If a haemoglobin concentration of 94g/L or less has been measured, and other inclusions/exclusions make the patient eligible, they can be approached for consent. Several scenarios based on the haemoglobin concentration may occur:

- a. The patient provides consent without any further haemoglobin measurement being undertaken for clinical or other reasons. In this situation the patient should be immediately randomised and managed according to the allocated group. There is no requirement to wait for the result of the baseline blood sample Hb measurement or any other Hb measurements before transfusing according to the protocol because the patient has demonstrated eligibility during the eligibility period.
- b. If the patient has been randomised, baseline blood samples have been taken, and the baseline or another Hb measurement becomes available before any transfusion has occurred, transfusion decisions should follow the protocol and group allocation using the most recent Hb concentration. The patient should remain in the trial once randomised and not be withdrawn if the Hb concentration is above 94 g/L on repeat Hb measurement. Transfusions should follow the protocol according to the most recent Hb measurement: for example if the Hb has increased on the baseline blood and is 94-99 g/L the patient should receive 1 unit of RBC if they are in the liberal group, with a target Hb of 100-120g/L. If they are in the restrictive group their Hb should simply be monitored, but they should not be withdrawn.
- c. If a patient is being screened and fulfils all eligibility and no exclusion criteria, *but has not yet provided consent* (for example lack of capacity or patient/family are still considering taking part) the following should guide participation:

- i. If a further Hb concentration is taken for clinical reasons *prior to consent* being obtained, and the result is >94 g/L, the patient is no longer eligible for the trial at that time.
- ii. If after (i) above, a further Hb concentration is taken for clinical or other reasons and is again ≤94 g/L the patient is again eligible if within the 7 days recruitment window. They can then be approached for consent.

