6.1.3 Deviations from the allocated transfusion practice

All deviations from the recommended transfusion practice should be reported as a protocol deviation on the appropriate protocol deviation form. The following are pre-defined deviations:

- Failure to re-check Hb concentration within 48 hours of a transfusion
- Failure to administer a blood transfusion within 48 hours of the stated trigger in the allocated group (<70g/L or <100g/L)
- In the usual care group, administration of a blood transfusion at a trigger Hb ≥70g/L without the responsible clinician providing a reason for modifying the transfusion trigger.

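### Minor: the Summary omits the Hb ≥100 g/L exception for the first unit, the sample-time 48-hour clock misfits a first unit given on an old qualifying Hb, and 7.3 lists units by date only

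*Protocol*

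**What the plan says.** **First unit.** The Summary (Treatment groups, intervention) states: "All patients will receive a single unit RBC transfusion post-randomisation". Section 6.1.2.3, which governs each Hb measured in the intervention period, states: "If the haemoglobin concentration is ≥100g/L no transfusion should be given". Section 5.1.3b covers the patient whose new Hb arrives after randomisation but before any unit: "transfusion decisions should follow the protocol and group allocation using the most recent Hb concentration". Its worked example covers 94-99 g/L and goes no higher.

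**Clock.** Section 6.1.2.4 asks for the unit within 48 hours of the triggering result and dates that result by "the time the sample was taken as per the laboratory report". It continues: "Transfusions that do not occur or occur after 48 hours will be considered a protocol deviation". Section 6.1.3 lists as a pre-defined deviation: "Failure to administer a blood transfusion within 48 hours of the stated trigger in the allocated group". For a patient who consents with no further Hb taken, 5.1.3a directs immediate randomisation and adds: "There is no requirement to wait for the result of the baseline blood sample Hb measurement or any other Hb measurements before transfusing". The qualifying Hb may be any in the eligibility period, and 5.1.2 says of that period: "The eligibility window will be from the time the patient meets inclusion criteria and has no exclusion criteria for up to seven days", counted from the decision that the patient is ready to leave ICU.

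**Record.** Section 7.3 lists every Hb with date and time, but red cell transfusions with date and number of units only. Two of the three pre-defined deviations in 6.1.3 depend on 48 hours measured to or from a unit.

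**The concern.** Two statements about the first unit cannot both be followed for an intervention patient whose Hb has risen to 100 g/L or more before transfusion. A site that follows the Summary gives a unit that 13.4.1.1 would class as a deviation. A site that follows 6.1.2.3 gives none.

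Separately, a site that does exactly what 5.1.3a asks can be late by the 6.1.2.4 clock, because that clock may have started before the patient was randomised. No sentence gives the first unit its own starting point.

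Finally, the data listed in 7.3 cannot always settle whether the 48-hour limits were met. Protocol compliance is a named process outcome (2.3.2, item 12), and 9.2 plans an efficacy estimate in fully compliant patients. Both depend on deviations being defined and recorded in the same way everywhere.

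**Working it through.** The plan gives no figure on this point beyond the 48-hour limit and the Hb thresholds, so the check is a comparison of rules and some calendar arithmetic.

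**1. Who gets the first unit.** Entry requires Hb ≤94 g/L (4.2). The Summary and 6.1.2.3 conflict only at Hb ≥100 g/L. The rise needed before the first unit is 100 − 94 = 6 g/L or more. From 94 to 99 g/L the Summary, 5.1.3b and 6.1.2.3 all give one unit. At 100 g/L and above the body sections agree on none, and only the Summary sentence differs.

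**2. First-unit clock.** Reading 6.1.2.4 literally, with no Hb newer than the qualifying one:

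hours left at randomisation = 48 − age of qualifying sample

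| Age of sample (h) | Hours left |
|---|---|
| 24 | 24 |
| 36 | 12 |
| 48 | 0 |
| 72 | −24 (already overdue) |

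From an age of 48 hours, even an immediate unit is late. How often this happens is not in the protocol. Section 7.2 requires a baseline Hb for all participants, accepts an existing result only if less than 24 hours old, and asks for research samples before any transfusion whenever possible. The case therefore needs an old qualifying Hb and a unit given before any fresher sample is drawn.

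**3. Date-only records.** Let the triggering sample be drawn t hours after midnight on day 0, and the unit be given at an unknown minute of day k. Elapsed time runs from 24k − t to just under 24k + 24 − t.

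- k = 0 or 1: at most 47.98 h (sample 00:00, unit 23:59 the next day), so always within the limit.
- k = 3 or more: at least 48.02 h (sample 23:59, unit 00:00 on day 3), so always beyond it.
- k = 2: over all sample times, 24.02 to 71.98 h. The range spans the limit for 1439 of the 1440 possible sample minutes. A 06:00 sample gives 48 − 6 = 42 to 72 − 6 = 66 h. A 10:00 sample gives 38 to 62 h.

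The same holds for the re-check. An Hb at 10:00 two days after the date of a unit was taken between 24 + 10 = 34 and 48 + 10 = 58 h after it.

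Assume, for illustration, that sample times are spread evenly over the day. For a true delay of d hours, the share of units dated day +2 is (d − 24)/24 for d from 24 to 48, and (72 − d)/24 for d from 48 to 72.

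| True delay (h) | Share not classifiable |
|---|---|
| 24 or less | 0% |
| 30 | 25% |
| 36 | 50% |
| 48 | 100% |
| 60 | 50% |
| 72 | 0% |

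Prompt units are never in doubt. The loss is greatest at the limit itself.

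**The case against.** **The intent is clear.** The same Summary paragraph gives the intervention trigger as below 100 g/L, 3.3.1 repeats it, and the body sections agree. The conflict is also narrow: a repeat Hb above 94 g/L before consent removes eligibility (5.1.3c), and randomisation follows consent at once. This stands. A reader might infer that the protocol leaves the treatment rule open or that sites are in fact treating differently. The documents support neither; the fault is one unconditional sentence in the Summary.

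**The qualifying Hb may not be the trigger at all.** Section 6.1.2.3 covers measurements in the intervention period, which starts at enrolment (6.1.1), and 6.1.3 speaks of the trigger in the allocated group, which does not exist before randomisation. That reading is fair. It leaves a first unit given on the older Hb with no stated clock, so a sentence is still needed. A reader might infer that correct first units are often logged as late. The baseline Hb rules in 7.2 point the other way.

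**Deviations are not derived from 7.3.** Sites report them on a dedicated form (6.1.3) and log (13.4.1.3), with the medical record among the sources (7.5), and the case report form (7.6) is not shown. This also stands. It would be too strong to say that the 48-hour deviations cannot be determined. What cannot be done is to check them from the listed fields when the dates are two days apart.

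**Restarting every first-unit clock at randomisation would loosen a working limit.** A 23-hour-old sample would then allow nearly 23 + 48 = 71 hours. This is correct, and the fix is limited accordingly.

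**Conclusion.** A minor point: wrong as written and cheap to improve. The Summary sentence contradicts 6.1.2.3 at Hb ≥100 g/L. The sample-time clock can literally mark a first unit directed by the protocol as late once the qualifying Hb is 48 hours old. The fields listed in 7.3 cannot settle the limit at a two-day date gap.

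The reach is limited to consistency of treatment, the protocol-compliance outcome and possibly the full-complier estimate, whose definition may be given in the SAP. The frequency of each situation is unknown, and the second is probably rare. The percentages above rest on an assumed even spread of sample times. They describe the calendar and do not estimate deviation rates. The third part assumes that the case report form holds no start time; if it does, only 7.3 needs aligning.

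A reader might go on to doubt the primary result. Nothing here supports that: the primary analysis is by intention to treat, and neither it nor the sample size uses these rules.

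**What to change.** One amendment with three changes:

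1. **Summary:** *one unit after randomisation unless the most recent Hb is ≥100 g/L*.
2. **Sections 6.1.2.4 and 6.1.3:** when the only triggering Hb was taken 24 hours or more before randomisation, the first-unit limit runs from randomisation. In all other cases it runs from the sample time, as now. This leaves the limit unchanged for samples that meet the 24-hour rule in 7.2.
3. **Section 7.3:** add the start time of each unit from now on, or align the list if the case report form already holds it. No look-back at earlier patients is required.

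The cost is the amendment wording, at most one extra field, and slightly changed deviation counts. Amendment 9 already made a wording correction of this kind to the Hb range in 5.1.3b.

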6.1.3 Deviations from the allocated transfusion practice

All deviations from the recommended transfusion practice should be reported as a protocol deviation on the appropriate protocol deviation form. The following are pre-defined deviations:

- Failure to re-check Hb concentration within 48 hours of a transfusion
- Failure to administer a blood transfusion within 48 hours of the stated trigger in the allocated group (<70g/L or <100g/L)
- In the usual care group, administration of a blood transfusion at a trigger Hb ≥70g/L without the responsible clinician providing a reason for modifying the transfusion trigger.

6.1.4 Use of alternatives to blood transfusion

Patients in both study groups can receive alternatives to blood transfusion if directed by the clinical teams. However, these should be consistent with current NICE guidance concerning alternatives to blood transfusion: (see: www.nice.org.uk/quidance/ng24)

6.1.5 Other treatment and interventions during the intervention period

All other treatments and therapies provided to patients in both study groups should be at the discretion of the clinical teams.

6.2 LONG TERM FOLLOW UP ASSESSMENTS

Following randomisation, assessment will be carried out at the following time points (see also table 1) irrespective of whether the patient remains in the acute hospital (intervention still ongoing) or has been discharged from the acute hospital (intervention period completed).

For all follow up visits, vital status should be confirmed and telephone contact made at the start of the visit window to alert the participant to the follow up and arrange a suitable time and method. To promote completeness the Physical Component Score (PCS) of the SF-36 should be done at this initial telephone contact wherever possible, especially at 90 day follow up.

If a participant opts for postal or online follow up, the local research team should check 7 days after the visit window opens that questionnaires have been completed. If questionnaires are not complete, the research team should contact the participant and offer to complete via the telephone or online with assistance given over the phone if required. A second telephone call should be undertaken to remind the participant if the first telephone call does not result in the participant returning the questionnaire.

30 day follow up (7 days prior or 14 days post visit date for all aspects of the follow-up visit). Ideally this visit will be conducted in person to allow blood sample collection. Arrange this visit with the participant before discharge if possible. In the event the participant declines blood sample, conduct visit remotely using the methods below.

- Vital status* and follow up to be carried out by the local research team.
- Follow up questionnaires
- o Data collection
- Blood sampling

90 day follow up (+/- 14 days) - prioritise primary outcome

- Vital status* will be checked and confirmed by the local research team. Follow up questionnaires will be undertaken by the local research team (or delegated individual).
 - Completion order as follows to ensure primary outcome is collected:
 - 1. Physical Component Score (PCS) of the SF-36
 - 2. Mental Component Score (MCS) of the SF-36
 - 3. Fatigue Severity Scale (FSS)
 - 4. WHODAS ADLs questionnaire
 - 5. Health Service Utilisation

Participants should be offered several ways in which to complete and return the follow up questionnaires:

- 1. **Telephone call** the participant can complete with the aid of a member of the trial team. *This is the preferred method.*
- 2. **Postal** questionnaires will be posted out to participants for completion and return in provided envelope.
- 3. **Online** can be answered directly onto the trial database via a link provided by the central research team.

180 days follow up (+/- 14 days)

- Vital status* will be checked and confirmed by the local research team.
- Follow up questionnaires completion will be undertaken by the local research team.
 - ➤ Completion order as follows to ensure primary endpoint is reached wherever possible:
 - 1. Physical Component Score (PCS) of the SF-36
 - 2. Mental Component Score (MCS) of the SF-36
 - 3. Fatigue Severity Scale (FSS)
 - 4. Health Service Utilisation
- Make telephone contact with the participant at the start of the visit window to alert them to the follow up and confirm the method. Wherever possible complete follow up questionnaires at this call.

Participants will be offered several ways in which to complete and return the follow up questionnaires:

- 1. **Telephone call** the participant can complete with the aid of a member of the trial team. *This is the preferred method.*
- 2. **Postal** questionnaires will be posted out to participants for completion and return in provided envelope.
- 3. **Online** can be answered directly onto the trial database via a link provided by the central research team.

For postal and online follow-up the research team should check whether this has been completed after 7 days and attempt to prompt completion whenever possible.

Follow up with the participant will occur within a 14 day window however, questionnaires may be returned outwith this window. Questionnaires returned after 14 days will not be classed as a deviation.

Five-year follow up will be completed via data linkage. This will only be undertaken if deemed worthwhile after the main trial analysis.

*At all follow ups, before contact is with the participant is attempted, survival status will be confirmed by the participating site using local health records/systems.

Table 1: Follow-up time points and measurements

	able 1: Follow-up time points and measurements Follow-up time point Measurements Comments		
rollow-up tillle pollit	Measurements	Comments	
30 days post	Physical Component Score (PCS) of the SF-36	Follow-up can be undertaken in	
randomisation (7 prior		any clinic (eg post-ICU follow-up	
or 14 days post visit		clinic; routine follow-up clinic)	
date) ¹	4. New Infections (defined as any clinically suspected or proven infection occurring after	or	
	randomisation requiring a new course of antibiotics)	In a clinical Research Facility	
(surviving patients)	5. Major Adverse Cardiac Events (MACE), comprising: any confirmed stroke, myocardial	or	
	infarction, or cardiovascular death	In the patients home or current	
	6. Transfusion-related adverse events	residence	
	Haemoglobin concentration	or	
		In a hospital ward	
	2. Blood samples for erythrogenesis and inflammatory markers (for patients providing		
	permission for this and where feasible to collect)	Follow up undertaken by local	
		investigator team	
	Health service utilisation questionnaire		
90 days post	Physical Component Score (PCS) of the SF-36	Follow up by postal questionnaire	
randomisation (±14	2. Mental Component Score (MCS) of the SF-36	followed by telephone consultation	
days)¹		if required	
	4. WHODAS ADLs questionnaire		
(surviving patients)	5. New Infections (defined as any clinically suspected or proven infection occurring after		
	, ,	consulting electronic health record	
	6. Major Adverse Cardiac Events (MACE), comprising: any confirmed stroke, myocardial		
	infarction, or cardiovascular death		
		Follow up undertaken by local	
		investigator team	
	9. Health service utilisation questionnaire		

180 days pos		Follow up by postal questionnaire
randomisation (±14 days) ¹	, ,	followed by telephone consultation if required
uays).	4. Survival	ii required
(surviving patients)		Survival determined by local team consulting electronic health record
		Follow up by local investigator
5 years pos		team Five-year outcomes determined by
randomisation ²	Health care resource and costs (via data linkage)	data linkage without needing to contact patients.

¹ If follow up in person is not possible or feasible, or is declined by the patient, then research teams should make efforts to obtain questionnaire data either by postal questionnaire or via telephone.

² the decision to undertake data linkage will be determined based on the results of the main trial and any effects seen.

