2.3.2 Secondary Endpoints/Outcomes

Patient centred outcomes:

- 1. Physical Component Score (PCS) of the SF-36 HRQoL questionnaire (and its four sub-domains) at 30 and 90 days post-randomisation.
- 2. Patient fatigue (Fatigue Severity Scale (FSS)) at 30, 90 and 180 days post-randomisation
- 3. Mental component score SF-36 (and its four sub-domains) at 30, 90 and 180 days post-randomisation.
- 4. Activities of Daily Living (ADLs) (WHODAS questionnaire⁴) at 90 days post-randomisation
- 5. Patients alive at 30, 90 and 180 days post-randomisation
- 6. Patients alive at 5 years post-randomisation derived from data linkage
- 7. Haemoglobin concentration at 30 days post-randomisation

Resource use and cost-effectiveness (based on data linkage and questionnaires):

- 8. Post-ICU length of hospital stay;
- 9. Care costs during 180 days post-randomisation.

- 10. Incremental cost per QALY at 180 days
- 11. Care costs derived from data linkage during 5 years post-randomisation (depending on results from shorter term outcome analysis)

Process and Safety outcomes:

- 12. Protocol compliance (during intervention index hospital stay)
- 13. Hb concentration (during index hospital stay)
- 14. RBC use (during 90 days follow up)
- 15. New Infections (during 90 days follow-up)
- 16. Transfusion-related adverse events (during 90 days follow-up)
- 17. Major adverse cardiovascular events (MACE; during 90 days follow-up)

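### Vital status is checked when the follow-up window opens (day 76 and day 166), so deaths on days 167–180 may be counted as alive at 180 days, and the end of the 90-day safety period is not fixed

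*Protocol*

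**What the plan says.** Section 6.2 sets one rule for all follow-ups: "vital status should be confirmed and telephone contact made at the start of the visit window". A footnote adds that, before contact is attempted, "survival status will be confirmed by the participating site using local health records/systems". The windows run 14 days either side of day 90 and day 180, and from 7 days before to 14 days after day 30. The opening call is meant to alert the participant and agree a time and method. Sites are also asked to complete the SF-36 PCS at that call where they can, above all at 90 days. At 180 days this extends to the follow-up questionnaires in general.

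The outcomes in section 2.3.2 refer to fixed days or periods: "Patients alive at 30, 90 and 180 days post-randomisation", and for safety "New Infections (during 90 days follow-up" and "Major adverse cardiovascular events (MACE; during 90 days follow-up"; transfusion-related adverse events have the same 90-day period.

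Table 1 lists infections and MACE in the 90-day row without naming a day within the window. For 180 days it takes survival from the electronic health record and gives no look-up date. Section 10.2.2 says that important events plausibly linked to the intervention are recorded over 180 days after hospital discharge. The five-year linkage is undertaken only if judged worthwhile after the main analysis. Section 9.2 plans a Cox model for mortality, and section 9.2.1 plans cost per QALY and cost per life-year at 180 days.

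**The concern.** A status read on day 166 shows that the patient was alive on day 166. The outcome asks about day 180. A site that does as section 6.2 says, and reaches the patient at the opening call, can finish the 180-day follow-up two weeks before the day the outcome describes. Nothing in section 6.2 or the legible part of Table 1 sends the site back. The same feature exists at 30 and 90 days, but there a later scheduled check follows.

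For the safety outcomes the difficulty is different. The period is stated as 90 days, the contact can fall anywhere in a 28-day window, and no instruction says to read the record to day 90 exactly. If sites collect events at the contact, the length of observation depends on when the patient was reached.

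At stake are the proportion alive at 180 days, the health-economic quantities built on 180-day survival, and whether the 90-day safety counts cover the same period for every patient.

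**Working it through.** **Window openings** (section 6.2)

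- 30-day visit: 30 − 7 = day 23
- 90-day visit: 90 − 14 = day 76; closes 90 + 14 = day 104
- 180-day visit: 180 − 14 = day 166

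Days between the opening check and the target day: 14 of 90 (14/90 = 15.6%) and 14 of 180 (14/180 = 7.8%).

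**Which gaps a later scheduled check closes**

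- Deaths on days 24–30 can be found at the 90-day check.
- Deaths on days 77–90 can be found at the 180-day check, if the date of death is recorded.
- Deaths on days 167–180 have no later scheduled check. Only the conditional five-year linkage remains.

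**Illustration of the number of deaths**

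Section 9.1 reports 12 deaths among 182 patients. 12/182 = 0.0659, which reproduces the stated 7% after rounding. The follow-up time behind this figure is not given, so two horizons T are used (90 and 180 days), with two assumed shapes for the timing of deaths. The planned sample size is 346.

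Expected deaths between window opening and target day = 346 × [S(opening) − S(target)], with S(T) = 1 − 0.0659.

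- Constant hazard: S(t) = exp(−ht), h = −ln(1 − 0.0659)/T = 0.0682/T
- Early-clustered deaths (Weibull, shape 0.5): S(t) = exp(−λ√t), λ = 0.0682/√T

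Worked case, constant hazard, T = 180: h = 0.000379; S(166) = 0.93904; S(180) = 0.93407; 346 × 0.00497 = 1.7.

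| Assumption | Days 76–90 | Days 166–180 | All deaths to day 180 |
|---|---|---|---|
| 12/182 by day 90, constant hazard | 3.4 | 3.2 | 44.1 |
| 12/182 by day 180, constant hazard | 1.8 | 1.7 | 22.8 |
| 12/182 by day 90, early-clustered | 1.8 | 1.2 | 31.8 |
| 12/182 by day 180, early-clustered | 1.3 | 0.9 | 22.8 |

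The exposed 180-day deaths therefore number about 0.9 to 3.2. As a share of all deaths to day 180 the extremes are 0.9/22.8 = 4% and 1.7/22.8 = 7%. These figures suppose that every patient is last checked on day 166; any later contact reduces them.

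**Carry-over to life-years.** Each such death counted as alive to day 180 adds at most 14 days, or 14/365 = 0.04 life-years. For three deaths that is about 0.12 life-years across the whole trial.

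**Safety events.** If events are collected at the contact, observation ends between day 76 and day 104. The protocol gives no rates for MACE, infection or transfusion reactions, so no number of lost or added events can be derived. Section 2.3.2 gives 90 days of follow-up and section 10.2.2 gives 180 days after hospital discharge. These are different periods with different starting points.

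**The case against.** The strongest reply is that the start-of-window check is there to avoid contacting the family of someone who has died, and is not the outcome assessment. Table 1 lists survival separately as a 180-day measurement from the electronic record, and a sensible site would look on the day. The Cox model can also censor at the last status check. Part of this stands: time-to-event analysis with proper censoring is largely protected. But Table 1 names no look-up date, the only timing rule in the text is the early one, and censoring does not supply an answer to whether the patient was alive at day 180. An analysis plan can truncate events by date; it cannot recover events that nobody was told to look for.

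A reader might infer several stronger things that the protocol does not support:

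- *That safety events are checked when the window opens.* The sentence in section 6.2 covers vital status and a telephone contact only. Safety events may be collected at any time in the window.
- *That deaths on days 77–90 are lost.* They can be found by date at the 180-day check.
- *That safety events on days 77–90 are never collected.* Section 10.2.2 describes a longer recording period. The copy of Table 1 used here is not fully legible, so an item not seen there is not evidence of omission.
- *That 16% of safety events are missed.* This needs a constant event rate and closure of every patient's data on day 76. A constant rate is implausible for transfusion reactions, since the allocated transfusion strategy ends at acute hospital discharge.
- *That the loss differs by arm.* Windows, staff and procedures are the same in both groups. The trial is open-label, but nothing in the protocol points to different contact timing.

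Counting events from days 91–104 is also not laid down by the protocol: the outcomes are bounded at 90 days, and a date rule in the case report form or analysis plan would enforce that.

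**Conclusion.** The point holds in a limited form. Section 6.2 fixes the vital status check before the day to which the survival outcome refers. At 180 days no unconditional later check closes the gap, so deaths on days 167–180 may be counted as alive at 180 days and carried into the 180-day life-year and QALY results. The illustrative size is about 1 to 3 deaths among 346, resting on 12/182 applying by day 90 or by day 180, on the two assumed timings of death, and on a last check at day 166 for everyone. That is small, and its effect on life-years is very small, but deaths are few enough that the 180-day survival proportion should not carry an avoidable error.

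For the 90-day safety outcomes the finding is one of definition: the day on which observation ends is not fixed, and sections 2.3.2 and 10.2.2 disagree on the recording period. No loss can be quantified. The primary outcome is not affected.

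**What to change.** Keep the questionnaire timing and the vital status check before contact. Then amend section 6.2 and Table 1 as follows:

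1. Survival for the 180-day outcome is read from the health record on or after day 180, and the date of the look-up is recorded.
2. Survival and the record check for MACE, new infections and transfusion-related events for the 90-day outcomes are done, or repeated, on or after day 90.
3. The date of each death and event is recorded, and only those dated up to the target day count towards the outcome.
4. Section 2.3.2, Table 1 and section 10.2.2 are reconciled so that one safety recording period is stated, with one starting point.

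The cost is a wording change, a date rule on the case report forms, and one extra look at local records per patient at each of the two time points by the same team. No additional patient contact is needed. The downside is a little more site time.
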